STUDY PROTOCOL

Title: Title: The Effectiveness of a Whitening and Anti-Aging Bilayering Serum and Cream Containing Gamma-Aminobutyric Acid (GABA) 3%, Dimethylaminoethanol (DMAE) 2%, Cysteamine 2.5%, and Bakuchiol 1%

NCT Number: NCT ID not yet assigned

Document Date: February 10th, 2025

This study was experimental research with a double blind randomized controlled clinical trial design conducted at the Department of Dermatology & Venereology and Hasanuddin University Hospital, Makassar City, South Sulawesi, Indonesia, from March to August 2025. This study was approved by the Health Research Ethics Committee, Faculty of Medicine, Hasanuddin University, Makassar, with number 93/UN4.6.4.5.31/PP36/2025.

Subject

The total number of subjects was 44, female, aged between 30-50 years, and Fitzpatrick skin type III-V. All participants in the study signed an informed consent form. The exclusion criteria were pregnancy, breastfeeding, menopause, using hormonal contraception skin, being treated with topical and systemic whitening agents for 1 month before the study began, and had a history of GABA, DMAE, Bakuchiol, or Cysteamine allergic reaction.

Study Protocol

Baseline melanin index (MI), L-value, and UV spot values were measured using Mexameter®, Chromameter®, and Janus-III Facial Analysis System® tools at week 0. In the morning (between 05:00–08:00 Central Indonesia Time), one group cleansed their face using five drops of facial wash, followed by the application of two drops of serum containing GABA 3%, DMAE 2%, Bakuchiol 1%, and Cysteamine 2.5% on both palms. The serum was then applied evenly over the entire face until fully absorbed and left on for one minute. A cream containing the same active ingredients (GABA 3%, DMAE 2%, Bakuchiol 1%, and Cysteamine 2.5%) was applied in an amount equivalent to one fingertip unit (FTU) to the whole face. In the evening (between 19:00–22:00), after cleansing the face again with five drops of facial wash, the same procedure was repeated—application of two drops of the active serum, followed by one FTU of the corresponding cream over the entire face.

In contrast, the other group followed an identical regimen using placebo products. In the morning (05:00–08:00 Central Indonesia Time), participants cleansed their face with five drops of facial wash, then applied two drops of placebo serum on both palms and spread it evenly over the entire face until absorbed, allowing it to rest for one minute. This was followed by the application of one FTU of placebo morning cream over the entire face. In the evening (19:00–22:00), after cleansing with five drops of facial wash, participants applied two drops of placebo serum and then one FTU of placebo night cream, following the same procedure as the morning routine. The subjects were randomly allocated into two groups: the treatment group (Group A) and the control group (Group B). Both participants and investigators were blinded to group allocation.

The Mexameter® MX 18 (Courage Khazaka, Germany) used 16 LEDs to emit light at three wavelengths: 568 nm (green), 660 nm (red), and 880 nm (infrared). The melanin index (MI), which corresponds to the skin melanin level, and the erythema index (EI) were obtained using a computerized examination. The Chromameter® (Konica Minolta, Japan) objectively measured skin color by analyzing the reflection of a xenon lamp perpendicular to the probe at 450 nm, 560 nm, and 600 nm. The resulting parameters were represented by the numbers L, a, and b. The L-value parameter represented the brightness of the skin colour (100 for white and 0 for black). The Janus-III Facial Analysis System® (PIE Inc, South Korea) was a facial analysis system that uses a high-resolution camera to objectively assess various skin issues such as pigmented spots, wrinkles, skin tone, UV spots, and sebum production. All data were analyzed using Statistical Package for Social Sciences (SPSS) version 22.0 (SPSS. Inc) with Unpaired Parametric T-Test was used for normally distributed data, while the Mann–Whitney test was applied for non-normally distributed data. Results were considered statistically significant at $p < 0.05$. All data results were presented in tables and graphs.

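### The plan names only two-sample tests without a baseline covariate and does not say whether final values or changes are compared; ANCOVA on the week-0 value would be at least as precise under either reading

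*Combined protocol and SAP*

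**What the plan says.** The Study Protocol section of the combined protocol and SAP opens with the baseline assessment: "Baseline melanin index (MI), L-value, and UV spot values were measured using Mexameter®, Chromameter®, and Janus-III Facial Analysis System® tools at week 0". Its last paragraph gives the whole of the statistical analysis, which is that an "Unpaired Parametric T-Test was used for normally distributed data, while the Mann–Whitney test was applied for non-normally distributed data", judged at the 0.05 level.

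The Subject section gives the sample: "The total number of subjects was 44, female, aged between 30-50 years, and Fitzpatrick skin type III-V". Women are randomised to two groups; neither an allocation ratio nor stratification is stated.

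The documents name no covariate, change score, adjusted estimate or confidence interval. They also give no follow-up week, effect size, SD, power or correlation between the week-0 and later values.

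**The concern.** Eligibility covers Fitzpatrick types III to V, while melanin index and L-value measure skin pigment and brightness directly. Women will therefore differ in these measures before any product is applied. If final values are compared without adjustment, that variation goes into the error term, and any chance difference between the groups at week 0 carries through to the result in proportion to the correlation. If changes are compared, the baseline is used, but with its slope fixed at 1, which over-corrects whenever the correlation is below 1.

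The plan does not say which of these is intended. The precision of a 44-subject trial, and how far its estimate can be moved by who happened to be darker at week 0, therefore rest on an unstated choice. That choice could also be made after the data are seen.

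**Working it through.** The plan states no power or sample-size calculation, so there is no figure to reproduce.

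**Inputs from the documents.** 44 subjects; two randomised groups; significance level 0.05; week-0 values of three measures.

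**Assumptions.** 1:1 allocation (n = 22 per group); two-sided test; equal SD at both times, taken as 1; no dropout; correlation ρ between week-0 and follow-up values from 0.3 to 0.9; true effect 0.5 SD.

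**Step 1: variance per subject.** Final value: 1. Change: 2(1−ρ). ANCOVA: 1−ρ². ANCOVA relative to final values is therefore 1−ρ². Relative to change it is (1−ρ²)/[2(1−ρ)] = (1+ρ)/2.

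**Step 2: power.** The standard error is √(2/22) = 0.302 times the square root of the variance in step 1. Power comes from the noncentral t distribution, with 42 degrees of freedom for the two-sample tests and 41 for ANCOVA.

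| ρ | ANCOVA variance ÷ final value | ANCOVA variance ÷ change | Power, final value | Power, change | Power, ANCOVA |
|---|---|---|---|---|---|
| 0.3 | 0.91 | 0.65 | 37% | 28% | 40% |
| 0.5 | 0.75 | 0.75 | 37% | 37% | 46% |
| 0.7 | 0.51 | 0.85 | 37% | 55% | 62% |
| 0.8 | 0.36 | 0.90 | 37% | 73% | 77% |
| 0.9 | 0.19 | 0.95 | 37% | 95% | 96% |

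The ANCOVA column ignores the small average variance inflation from estimating the slope, (44−3)/(44−4) = 1.025. Including it lowers ANCOVA power by about one point or less and leaves the ordering unchanged in every row.

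**Step 3: detectable effect at 80% power.** The final-value test detects 0.865 SD. At ρ = 0.8, a change score detects 0.865 × √0.4 = 0.55 SD and ANCOVA 0.865 × √0.36 = 0.52 SD.

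**Step 4: chance imbalance (normal approximation).** The baseline difference has standard error 0.302 SD. It exceeds 0.3 SD in absolute value with probability 32%, and 0.5 SD with probability 10%.

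Take an imbalance of 0.5 SD, ρ = 0.8 and no treatment effect. Given the imbalance, each estimate has standard error √(1−0.64) × 0.302 = 0.181.

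- Final values: shift 0.8 × 0.5 = 0.40 SD. The critical difference is 1.96 × 0.302 = 0.591, and (0.591 − 0.40)/0.181 = 1.06. Conditional type I error is about 15%.
- Change: shift (0.8 − 1) × 0.5 = −0.10 SD. The critical difference is 1.96 × √0.4 × 0.302 = 0.374, and (0.374 − 0.10)/0.181 = 1.51. Conditional type I error is about 7%.

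Smaller imbalances offset this. At 0.3 SD and ρ = 0.8 the final-value figure is 2.6%. Averaged over all randomisations the rate is 5%.

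**The case against.** The strongest reply is that the stated tests are valid. Randomisation holds their type I error at 5% overall, and the 15% figure is conditional on an imbalance that arises about one time in ten. That stands: this is a matter of precision and conditional bias.

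Second, a reader might infer that the plan discards much of its power and leaves baseline imbalance uncorrected. The documents do not support this, because they never say that final values are tested. If changes are tested, the baseline is already used, and at the correlations where the gain over final values is largest the gain over change scores nearly vanishes: 4 points at ρ = 0.8 and 1 point at ρ = 0.9. Even against final values the gain is only 3 points at ρ = 0.3. The size depends on a correlation that the plan does not give.

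Third, a reader might infer that every outcome has a baseline. Week-0 values are stated for three measures only. The imaging system is described as able to "objectively assess various skin issues such as pigmented spots, wrinkles, skin tone, UV spots, and sebum production", but that is a device capability, and the plan never defines its outcome set.

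Finally, the plan provides for non-normal data, so a replacement that ignored non-normal residuals would be a step back. That also stands, and the fix covers it.

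**Conclusion.** The point holds in limited form. The tested quantity and time point are unspecified, no baseline adjustment is planned for three measures that have week-0 values, and ANCOVA would serve at least as well whichever quantity was meant. It also removes the need to guess the correlation: a change score is worse than final values below ρ = 0.5 and better above it, while ANCOVA is ahead of both across 0.3 to 0.9.

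For a 0.5 SD effect the gain in power is 3 to 59 percentage points over final values. Over change scores it is about 12 points at ρ = 0.3, falling to 1 at ρ = 0.9. These figures rest on 22 per arm, a two-sided test, equal SDs and no dropout, none of which the plan states. The change should be made because it costs almost nothing; without it the stated tests would still be valid.

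**What to change.** Replace the sentence naming the tests with:

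> For melanin index, L-value and UV spots, the treatment effect is the adjusted mean difference (A minus B) at the end-of-treatment visit [sponsor to state the week], with 95% CI, from ANCOVA with treatment group and the week-0 value of the same measure, including all randomised subjects with a measurement in their allocated group. If residuals are clearly non-normal, a transformed or rank-based ANCOVA is used.

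Keep the unpaired t-test or Mann–Whitney test as a sensitivity analysis, and state whether it is applied to final values or to changes. The sponsor must supply the follow-up week, since the documents give none.

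The cost is one paragraph of wording and one degree of freedom per model. No new data are needed, and ANCOVA is available in the SPSS version already named.

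### The observed data choose between a t-test and Mann–Whitney for each outcome; neither test uses the week-0 values as a covariate, and no effect estimate or confidence interval is named

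*Combined protocol and SAP*

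**What the plan says.** The whole analysis plan is the end of the last paragraph under Study Protocol in the combined protocol and SAP. The comparison rule has two branches: "Unpaired Parametric T-Test was used for normally distributed data", "while the Mann–Whitney test was applied for non-normally distributed data". The decision criterion is a p-value: "Results were considered statistically significant at" p < 0.05. Results are to go into tables and graphs, whose content is not described.

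The same section states "Baseline melanin index (MI), L-value, and UV spot values were measured" at week 0, so each outcome has a baseline value. The Subject section gives the size: "The total number of subjects was 44". On allocation the text says "The subjects were randomly allocated into two groups", without a ratio.

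The plan does not say how normality is judged: which check, at what level, on raw values or changes, per arm or on residuals. It does not say whether follow-up values or changes from baseline are compared, or whether tests are two-sided. It names no primary outcome, effect estimate or confidence interval.

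**The concern.** A t-test compares means. Mann–Whitney compares rank distributions, and it is a test of location only if the two arms have the same shape. If the data choose between them, the hypothesis for each outcome is known only after the data are seen. MI, L-value and UV spots may then be judged on different hypotheses within one report. At this sample size a normality check is a noisy instrument, so the branch taken is partly chance.

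Two further gaps sit in the same paragraph. The week-0 measurements do not enter either test as covariates, although in a small trial they are the cheapest source of precision. And with only a significance threshold stated, nothing commits the report to a size of effect in MI or L-value units, which a reader needs in order to judge whether a change is meaningful.

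**Working it through.** **Plan's own figure.** The total of 44 cannot be reproduced, because no power, effect size, SD or dropout rate is given.

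**Inputs from the document.** N = 44; two groups; three outcomes (MI, L-value, UV spots); alpha 0.05; the two tests.

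**Assumptions, because the document is silent.** 1:1 allocation, so 44 / 2 = 22 per arm; two-sided tests; Shapiro–Wilk at 0.05, either in each arm (one failure triggers the switch) or once on pooled residuals.

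**1. Switching when the data are truly normal.**
- Per outcome, residuals checked: 0.05, so 5%.
- Per outcome, each arm checked: 1 − 0.95² = 0.0975, about 10%.
- At least one of three independent outcomes: 1 − 0.95³ = 0.143 (residuals) to 1 − 0.95⁶ = 0.265 (each arm), about 14–26%.
- Correlation between outcomes changes the upper figure little: 24% at a correlation of 0.8.

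**2. Simulation.** 20,000 trials per scenario, 22 per arm, same shape in both arms. Disagree means that the t-test and Mann–Whitney fall on opposite sides of p = 0.05. The switching, type I error and first disagreement columns are from runs with no shift.

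| Shape | Switch, each arm | Switch, residuals | Type I error of the rule (each arm) | Disagree, no shift | Disagree, 0.85 SD shift |
|---|---|---|---|---|---|
| Normal | 9.9% | 4.8% | 5.3% | 1.8% | 5.5% |
| t, 5 df | 35.8% | 30.6% | 5.1% | 2.6% | 8.4% |
| Gamma(4) | 54.6% | 58.3% | 5.5% | 2.5% | 7.8% |
| Lognormal, sigma 0.3 | 47.0% | 48.3% | 5.5% | 2.4% | 7.8% |
| Lognormal, sigma 0.5 | 82.0% | 85.8% | 5.5% | 3.3% | 12.2% |
| Lognormal, sigma 0.8 | 98.3% | 98.8% | 4.9% | 4.0% | 16.5% |
| Exponential | 98.5% | 99.0% | 5.1% | 3.6% | 14.5% |

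Under mild skew the branch is close to a coin toss. Type I error stays at 4.9–5.5%; a separate run with negative binomial counts gave 5.7%.

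**3. The two branches test different things.** With equal means and SDs but different shapes (lognormal sigma 0.8 against normal), the rule went to ranks in 88% of trials and rejected in 7.8%. The t-test rejected in 5.5%.

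**4. What the unused baseline could be worth.** Detectable difference at 80% power, normal approximation, in SDs of the raw follow-up value:
- Raw follow-up values: (z₀.₉₇₅ + z₀.₈₀) × √(2/22) = 2.8016 × 0.3015 = 0.84 SD.
- ANCOVA multiplies this by √(1 − ρ²), where ρ is the baseline correlation (assumed). At ρ = 0.5: 0.8447 × 0.866 = 0.73 SD. At ρ = 0.8: 0.8447 × 0.6 = 0.51 SD.
- Change scores multiply it by √(2(1 − ρ)). At ρ = 0.5: 0.8447 × 1 = 0.84 SD. At ρ = 0.8: 0.8447 × 0.632 = 0.53 SD.

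If the plan means change scores, the gain from ANCOVA is therefore 0.84 to 0.73 SD at ρ = 0.5, but only 0.53 to 0.51 SD at ρ = 0.8.

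**The case against.** **The rule does little statistical harm, and under skew it helps power.** This stands. Type I error is close to nominal. At a 0.85 SD shift with lognormal data (sigma 0.5), the rule rejected in 89.7% of trials against 79.3% for an always-used t-test. A reader might infer that choosing the test from the data seriously inflates alpha; the figures do not support that. Taking the smaller of the two p-values would give 5.9–6.6%, but nothing in the plan permits that choice. The power result is a reason to pre-state a log scale or count model for a skewed outcome.

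**A rule is written down, and the document is dated before the study's stated start in March 2025.** Also true. It would be wrong to say that nothing is pre-specified. But without a normality criterion the rule does not determine the analysis, and stating one would still leave the hypothesis dependent on the data.

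**The baseline and reporting gaps are not caused by the normality rule.** This stands too. A reader might infer that only the rank branch forgoes baseline adjustment and an effect size. The planned unpaired t-test does not adjust either, and no estimate is named for either branch. Mann–Whitney can be paired with a Hodges–Lehmann difference in the outcome's own units. These are gaps of the whole paragraph. The tables and graphs may contain estimates; the plan does not commit to them.

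**Different tests for the same outcome at two visits.** A reader might infer this as well, but week 0 is the only measurement time named, so the document gives it no footing.

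**Conclusion.** The point holds as a modest one about specification and efficiency. No single comparison per outcome is fixed in advance. The switching figures are a range, not a prediction: they rest on the assumed 22 per arm and Shapiro–Wilk check, and on exact normality. Real data with mild skew would make the branch far less predictable.

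The practical consequence is that the outcomes may not be comparable with each other, and that in some trials with a real effect (5.5–16.5% across the shapes tried, at 0.85 SD) significance would depend on which test was used. The precision gain from adjustment depends on a baseline correlation that the document does not give, and on whether raw values or changes are meant. The validity of the trial's type I error is not in question on this ground.

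**What to change.** Before unblinding, replace the normality-gated pair of tests with one stated analysis per outcome:

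- **MI and L-value:** ANCOVA on the follow-up value, adjusted for that outcome's week-0 value, reporting the adjusted mean difference with a heteroscedasticity-robust or bootstrap 95% CI.
- **UV spots:** the same model. If skew is expected, state a log scale or count model in advance. If log(x + 1) is used, describe the back-transformed result as a ratio of (spots + 1), not of spots.
- **Sensitivity:** Mann–Whitney with a Hodges–Lehmann difference and its 95% CI, labelled as such.
- **Reporting:** an estimate and 95% CI for every outcome, alongside the p-value.

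If unblinding has already happened, report these analyses next to the stated tests and say when they were chosen.

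The cost is a few sentences of plan text and modest extra analysis. No participant or measurement is added, and the covariate uses one degree of freedom (44 − 2 = 42 becomes 41). The downside is a slightly less simple presentation than one p-value per outcome.

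### Three unranked outcomes, no stated post-baseline assessment time and an unadjusted p < 0.05: the trial-wise false-positive rate is not controlled at 5%

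*Combined protocol and SAP*

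**What the plan says.** The document's title poses the question as effectiveness for whitening and anti-aging. The Study Protocol section then lists the measurements: "Baseline melanin index (MI), L-value, and UV spot values were measured using Mexameter®, Chromameter®, and Janus-III Facial Analysis System® tools at week 0". No outcome there, or anywhere else, is called primary or secondary. Week 0 is the only measurement time given. No follow-up week, number of visits or treatment duration appears. The March to August 2025 window is the period of study conduct, not a per-subject follow-up time.

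The last paragraph of the same section describes the devices and then the analysis. The groups are compared by an unpaired t-test or a Mann–Whitney test, depending on normality. The whole decision rule is "Results were considered statistically significant at $p < 0.05". There is no adjustment, no order of testing, and no statement of how many outcomes must succeed.

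The device descriptions mention further outputs. For the Mexameter, "the erythema index (EI) were obtained using a computerized examination". For the Chromameter, "The resulting parameters were represented by the numbers L, a, and b". The Janus system is said to "objectively assess various skin issues such as pigmented spots, wrinkles, skin tone, UV spots, and sebum production". The plan does not say whether any of these beyond MI, L-value and UV spots is analysed.

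**The concern.** With at least three outcomes and one threshold applied to each result, 5% is the error rate of a single test, not of the trial's conclusion. Because neither the lead outcome nor the visit is fixed, both could be settled after the results are known, and a reader could not tell a planned result from a selected one. A later correction cannot fully repair this, because the set of tests it would have to cover was never defined.

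**Working it through.** **Inputs from the document (Study Protocol section, and Subject section for N)**
- Threshold: 0.05 for each result, unadjusted.
- Outcomes: three named (MI, L-value, UV spots), unranked.
- Total N: 44, two groups, unpaired tests.

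**Assumptions, because the document is silent**
- Tests are two-sided.
- Allocation is 1:1, so 22 per group (used only in the simulation and in the detectable difference under the fix).
- There is one post-baseline visit.
- The outcomes share a common correlation r, varied over a range.
- Any one significant outcome would be taken as support for effectiveness.

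**Step 1. The plan's own figure.** For one outcome at one visit, 1 − 0.95^1 = 0.05. The stated 5% is correct for a single test. The plan states no trial-wise rate to reproduce.

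**Step 2. Three independent outcomes, one visit.**
- At least one two-sided false positive: 1 − 0.95^3 = 1 − 0.8574 = 14.3%.
- At least one false positive favouring the product (2.5% per test): 1 − 0.975^3 = 1 − 0.9269 = 7.3%.

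**Step 3. Correlated outcomes, one visit.** Unpaired t-tests were simulated under no effect, with 22 per group, 42 degrees of freedom and 20,000 trials per setting. Outcomes are coded so that positive means benefit.

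| r | Any two-sided false positive | Any false positive favouring the product |
|---|---|---|
| 0 (exact, step 2) | 14.3% | 7.3% |
| 0.3 | 13.5% | 7.0% |
| 0.5 | 12.7% | 6.5% |
| 0.7 | 10.9% | 5.6% |
| 0.8 | 9.8% | 4.8% |
| 0.9 | 8.7% | 4.5% |

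The simulation standard error near 12.7% is √(0.127 × 0.873 / 20,000) = 0.24 percentage points. Separate draws of correlated normal statistics (400,000) gave 12.5% at r = 0.5 and 9.7% at r = 0.8, which agrees.

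**Step 4. Ratio to nominal.** Two-sided: 14.3/5 = 2.9 and 9.8/5 = 2.0. Favouring the product: 7.3/2.5 = 2.9 and 4.8/2.5 = 1.9. On either count, the rate is about two to three times nominal for r from 0 to 0.8.

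**Step 5. Larger families, as scenarios only.**
- Three outcomes at two visits: 1 − 0.95^6 = 26.5% if all six tests are independent. It is about 16–22% for r from 0.8 down to 0.3, with an assumed correlation of 0.7 between visits.
- Ten device parameters at one visit (MI, EI, L, a, b, pigmented spots, wrinkles, skin tone, UV spots, sebum): 1 − 0.95^10 = 40.1% if independent, 28.7% at r = 0.5 and 17.2% at r = 0.8.

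**Step 6. Under the fix.** One primary outcome at one visit gives 5%. Holm across three starts at 0.05/3 = 0.0167, then 0.05/2 = 0.025, then 0.05, and keeps the familywise rate at or below 5%.

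**The case against.** The strongest reply is that the plan never says one significant outcome is enough. If all three had to be significant at one fixed visit, the trial-wise error would not exceed 5%. That is true, and the any-one-suffices rule is an inference. But no success rule is written, so the protective one cannot be assumed either.

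Three stronger readings are tempting, and the document does not support them.
- *The chance of a false claim of effectiveness is well above 5%.* The 10–14% figures count results in either direction, and a result favouring placebo could not support effectiveness. Counting only errors in the product's favour, the three-outcome, one-visit case gives about 5–7%. That is close to 5%, although the proper reference is 2.5%.
- *Several follow-up visits multiply the tests.* The text names only week 0, and a single later visit fits it equally well.
- *All ten device outputs are tested.* The list "pigmented spots, wrinkles, skin tone, UV spots, and sebum production" describes what the Janus system can assess, and EI, a and b also appear in device descriptions. The anti-aging part of the title makes a look at wrinkles plausible, but no text says these outputs serve as efficacy outcomes.

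Correlation between the outcomes is also a fair point. It reduces the inflation without removing it: at r = 0.9 the two-sided rate is still 8.7%. Finally, the missing assessment time is a defect in its own right and would matter even with one outcome.

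**Conclusion.** The concern holds in its minimum form: as written, the rule leaves the trial-wise false-positive rate uncontrolled at 5%. Its size is conditional on one visit, two-sided tests, 1:1 allocation, and a single significant outcome being accepted as support. It is then about 10–14% in either direction for correlations from 0.8 to 0. The step 5 figures show only what would follow if more visits or more device outputs were tested, and should not be cited as properties of this trial. This is more than missing detail, because the omitted rule decides what the trial may conclude, and a cheap, standard alternative is available.

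**What to change.** Before unblinding, add the following to the analysis paragraph:
- Name one of the three outcomes as primary, at one stated end-of-treatment visit that is the same for every subject, tested two-sided at 0.05. The choice is the sponsor's. MI would serve as an example, but nothing in the document favours it.
- Test the other two in a stated fixed order at 0.05, each only if the test before it is significant. Alternatively, use Holm across all three, starting at 0.0167.
- Report any other visits or device parameters as exploratory, with estimates and confidence intervals and no significance claims.
- Conclude effectiveness only if the primary test succeeds or, under Holm, only for the outcomes that pass.

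The document is dated before the study period but written in the past tense, so it does not show whether results have been seen. If they have, label the hierarchy post hoc and report every test performed.

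The cost is a few sentences, with no change to treatment, measurements or sample size. The price of a hierarchy is that a lone nominally significant secondary outcome can no longer carry the claim. The price of Holm is sensitivity. With 22 per group assumed and 80% power (normal approximation), the detectable difference is (1.960 + 0.842) × √(2/22) = 0.84 SD at 0.05. At Holm's first step it is (2.394 + 0.842) × √(2/22) = 0.98 SD.
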